## APPENDIX H. DEFINITION OF CD TREATMENT FAILURE AND INTOLERANCE

### Budesonide

- Failure is defined as having signs and symptoms of active disease despite a history of receiving  $\geq 8$  weeks of treatment with budesonide at doses  $\geq 9$  grams
- Intolerance: similar to systemic corticosteroids

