- Prior treatment with biologics for the treatment of CD (approved or investigational), other than infliximab, adalimumab, certolizumab or vedolizumab
- Prior treatment with more than 3 biologics for the treatment of CD (ie, infliximab, adalimumab, certolizumab or vedolizumab). Treatment with a biologic within 8 weeks prior to the Screening Visit, or 5 elimination half lives, whichever is longer. (See [Table 8](#) for elimination half-life timeframes of biologics.)

Permitted concomitant medications during the study include:

- Oral aminosalicylates (sulfasalazine [SSZ] or 5-aminosalicylic acid [ASA] compounds), provided that treatment has been given at a stable dose for at least 2 weeks prior to the Screening Visit. The dose of oral aminosalicylates must remain stable through the duration of the study or early termination from the study. If oral aminosalicylates have been recently discontinued, treatment must have been stopped at least 2 weeks prior to the Screening Visit.
- Oral corticosteroids, provided that the dose (prednisone  $\leq$  20 mg/day or equivalent, budesonide  $\leq$  9 mg/day) has been stable for 3 weeks prior to the Screening Visit. If oral corticosteroids were recently discontinued, discontinuation must have been completed at least 3 weeks prior to the Screening Visit. Corticosteroid doses should remain stable until the subject is eligible to start corticosteroid tapering, beginning at the Week 12 Visit (see Section 6.7 for details).
- Immunosuppressants, such as AZA, 6-MP, or MTX, provided that treatment was initiated  $\geq$  12 weeks prior to the Screening Visit, must be at a stable dose for  $\geq$  8 weeks prior to the Screening Visit and remain stable for the duration of the study. If immunosuppressants have been recently discontinued, treatment must have been stopped at least 8 weeks prior to the Screening Visit.
- Antibiotics used for the treatment of CD (eg, ciprofloxacin, metronidazole), provided that the dose has been stable for at least 2 weeks prior to the Screening Visit. If antibiotics have been recently discontinued, discontinuation must have been completed at least 2 weeks prior to the Screening Visit.
- Acetaminophen and low-dose aspirin for cardiovascular prophylaxis are allowed.

**Note:** The dose of concomitant CD medications noted above may not be increased above the baseline dose during the study. No new CD therapy can be prescribed once the subject has been screened in the study.

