### 4.2. Inclusion Criteria

Subjects must satisfy the following criteria to be enrolled in the study:

1. Subject is a male or female  $\geq 18$  years at the time of signing the informed consent form (ICF).
2. Subject must understand and voluntarily sign an ICF prior to conducting any study-related assessments/procedures.
3. Subject is willing and able to adhere to the study visit schedule and other protocol requirements.
4. Subject must have a diagnosis of CD with a duration of at least 3 months prior to the Screening Visit.
5. Subject must have ileitis, ileocolitis or colitis, as determined by ileocolonoscopy during screening.
6. Subject must have active CD disease, defined as a CDAI score  $\geq 220$  and  $\leq 450$  at screening.
7. Subject must have a 7-day average stool frequency  $\geq 3.5$  or abdominal pain  $\geq 1.5$  at screening.
8. Subject must have a total SES-CD  $\geq 6$  at screening, or the ileum segmental SES-CD  $\geq 4$  at screening.
9. Subject must have failed or experienced intolerance to at least one of the following: budesonide; systemic corticosteroids; immunosuppressants (eg, AZA, 6-MP, or MTX); or biologics for the treatment of CD (ie, infliximab, adalimumab, certolizumab or vedolizumab). (See [Appendix H](#) for details.)
10. Subject must meet the following laboratory criteria
  - a. White blood cell count  $\geq 3000/\text{mm}^3$  ( $\geq 3.0 \times 10^9/\text{L}$ )
  - b. Platelet count  $\geq 100,000/\text{mm}^3$  ( $\geq 100 \times 10^9/\text{L}$ )
  - c. Serum creatinine  $\leq 1.5 \text{ mg/dL}$  ( $\leq 132.6 \mu\text{mol/L}$ )
  - d. Aspartate aminotransferase (AST)/serum glutamic oxaloacetic transaminase (SGOT), alanine aminotransferase (ALT)/serum glutamic pyruvic transaminase (SGPT)  $\leq 2.5 \times$  upper limit of normal (ULN)
  - e. Total bilirubin  $\leq 2 \text{ mg/dL}$  ( $34 \mu\text{mol/L}$ ), unless the subject has a confirmed diagnosis of Gilbert's Disease
  - f. Hemoglobin  $\geq 8 \text{ g/dL}$  ( $\geq 4.97 \text{ mmol/L}$ )

- g. Activated partial thromboplastin time (APTT)  $\leq 1.5 \times$  ULN
11. Females of childbearing potential (FCBP) must have a negative pregnancy test at the Screening and Baseline Visits. While on IP and for at least 28 days after taking the last dose of IP, FCBP who engage in activity in which conception is possible must use one of the approved contraceptive options described below:

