### 4.3. Exclusion Criteria

The presence of any of the following will exclude a subject from enrollment:

1. Subject has a diagnosis of ulcerative colitis (UC), indeterminate colitis, ischemic colitis, microscopic colitis, radiation colitis or diverticular disease-associated colitis.
2. Subject has local manifestations of CD such as abscesses, short bowel syndrome, or other disease complications for which surgery might be indicated or could confound the evaluation of efficacy.
3. Subject had any intestinal resection within 6 months or any intra-abdominal surgery within 3 months prior to the Screening Visit.
4. Subject has an ileostomy or a colostomy.
5. Subject had prior treatment with mycophenolic acid, tacrolimus, sirolimus, cyclosporine, thalidomide or apheresis (eg, Adacolumn®) within 8 weeks prior to the Screening Visit.
6. Subject has received IV corticosteroids within 2 weeks prior to the Screening Visit.
7. Subject has changed or discontinued the dose of oral aminosalicylates within 2 weeks prior to the Screening Visit.
8. Subject has changed or discontinued the dose of oral corticosteroids (prednisone  $\leq 20$  mg/day or equivalent, budesonide  $\leq 9$  mg/day) within 3 weeks prior to the Screening Visit.

---

 A female of childbearing potential is a sexually mature female who 1) has not undergone a hysterectomy (the surgical removal of the uterus) or bilateral oophorectomy (the surgical removal of both ovaries) or 2) has not been postmenopausal for at least 24 consecutive months (that is, has had menses at any time during the preceding 24 consecutive months).

 A female of childbearing potential taking an oral contraceptive may need a backup or an alternative method of birth control based on Investigator judgment as the subject's Crohn's disease may potentially decrease the effectiveness of oral contraceptives.

9. Subject has initiated immunosuppressants (eg, AZA, 6-MP, or MTX) within 12 weeks prior to the Screening Visit and has changed or discontinued the dose of immunosuppressants within 8 weeks prior to the Screening Visit.
10. Subject has received topical GI treatments, such as, 5-aminosalicylic acid (5-ASA) or corticosteroid enemas or suppositories within 2 weeks prior to the Screening Visit.
11. Subject has received bile acid sequestrants (eg, cholestyramine) within 3 weeks prior to the Screening Visit.

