## 6.7. Corticosteroid Tapering Procedure

Subjects are eligible to start corticosteroid tapering beginning at the Week 12 Visit, at the discretion of the Investigator, according to the following schedule:

- For prednisone doses  $> 10$  mg (or equivalent), each week the daily dose is to be tapered by 5 mg until a dose of 10 mg/day is reached, after that each week the daily dose is to be tapered by 2.5 mg until discontinuation.
- For prednisone doses  $\leq 10$  mg (or equivalent), each week the daily dose is to be tapered by 2.5 mg until discontinuation.
- Subjects receiving budesonide should have their daily dose tapered by 3 mg every 3 weeks.

[Redacted text block]

[Redacted text block]

[Redacted text block]

[Redacted text block]

[Redacted text block]

CEL GENE PROPRIETARY INFORMATION

[Redacted text block]

[Redacted text block]

[Redacted text block]

[Redacted text block]

[Redacted text block]

CEL GENE PROPRIETARY INFORMATION

[Redacted]

[Redacted]

[Redacted]

CELGENE PROPRIETARY INFORMATION

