### 8.1. Permitted Concomitant Medications and Procedures

The following medications are allowed during the study:

- Oral aminosalicylates (SSZ or 5-ASA compounds), provided that treatment has been given at a stable dose for at least 2 weeks prior to the Screening Visit. The dose of oral aminosalicylates must remain stable through the duration of the study or early termination from the study. If oral aminosalicylates have been recently discontinued, treatment must have been stopped at least 2 weeks prior to the Screening Visit.
- Oral corticosteroids, provided that the dose (prednisone  $\leq$  20 mg/day or equivalent, budesonide  $\leq$  9 mg/day) has been stable for 3 weeks prior to the Screening Visit, and the dose must remain stable until the subject is eligible to start corticosteroids tapering (Section 6.7). If oral corticosteroids have been recently discontinued, discontinuation must have been completed at least 3 weeks prior to the Screening Visit.
- Immunosuppressants, such as AZA, 6-MP, or MTX, provided that treatment was initiated  $\geq$  12 weeks prior to the Screening Visit, must be at a stable dose for  $\geq$  8 weeks prior to the Screening Visit and remain stable for the duration of the study. If immunosuppressants have been recently discontinued, discontinuation must have been completed at least 8 weeks prior to the Screening Visit.
- Antibiotics used for the treatment of CD (eg, ciprofloxacin, metronidazole), provided that the dose has been stable for at least 2 weeks prior to the Screening Visit. If antibiotics have been recently discontinued, discontinuation must have been completed at least 2 weeks prior to the Screening Visit.
- Acetaminophen and low-dose aspirin for cardiovascular prophylaxis are allowed.

**Note:** The dose of concomitant CD medications noted above may not be increased during the study. No new CD therapy can be prescribed once the subject has been screened in the study.

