### Systemic corticosteroids

- Failure is defined as having signs and symptoms of active disease despite a history of receiving at least one 4-week course regimen with prednisone  $\geq 0.75$  mg/kg mg daily orally or equivalent, or 1 week of intravenous corticosteroids. Where regional or local practice standards for the use of steroids in CD differ from this definition of failure, the local or regional standard should be used.
- Intolerance includes, but is not limited to Cushing's syndrome, osteopenia/osteoporosis, hyperglycemia, insomnia and infection.

[figure not shown]

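### Appendix H sets the budesonide-failure threshold for inclusion criterion 9 in grams with no time basis, while every other visible budesonide dose in the protocol is in milligrams

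*Protocol*

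**What the plan says.** Inclusion criterion 9 (Protocol 4.2) reads: "Subject must have failed or experienced intolerance to at least one of the following: budesonide; systemic corticosteroids; immunosuppressants", with biologics completing the list, and refers to Appendix H for details. The budesonide entry in Appendix H defines failure as active disease despite at least 8 "weeks of treatment with budesonide at doses $\geq 9$ grams". It gives no per-day or cumulative basis. Its only link to the next entry concerns intolerance: "Intolerance: similar to systemic corticosteroids".

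The other visible budesonide doses in the protocol are:

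- Protocol Summary, permitted medications: "budesonide $\leq$ 9 mg/day) has been stable for 3 weeks prior to the Screening Visit"
- Section 4.3, exclusion criterion 8: "budesonide $\leq 9$ mg/day) within 3 weeks prior to the Screening Visit"
- Section 8.1: "budesonide $\leq$ 9 mg/day"
- Section 6.7: "Subjects receiving budesonide should have their daily dose tapered by 3 mg every 3 weeks"

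The systemic corticosteroid entry in Appendix H contains a clause deferring to local practice, which begins "Where regional or local practice standards for the use of steroids in CD differ from this definition of failure". The budesonide entry has no such clause. The visible SAP text gives no budesonide dose.

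**The concern.** The Appendix H entry is a decision threshold in current operative text, and no other visible text defines budesonide failure. The word grams is spelled out in running prose, so damage in text extraction is an unlikely explanation.

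Two people applying the entry to the same subject can reach opposite answers. One who follows the words will find that a subject with only a budesonide history on the protocol's own dose scale does not meet criterion 9. One who assumes a slip will find that the subject does. Protocol 15.1 requires monitors to verify adherence to the eligibility criteria. SAP Section 6 tabulates eligibility criteria failed among all screened subjects, and SAP Section 7 tabulates protocol violations and deviations. What is at stake is whether those tables rest on one rule.

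**Working it through.** The threshold is a stated definition with no derivation behind it, so there is no calculation in the plan to reproduce. The check is a unit conversion set against the protocol's other budesonide doses.

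**Inputs**

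| Quantity | Value | Source |
|---|---|---|
| Failure threshold | at least 9 g, no time basis | Appendix H, Budesonide |
| Minimum course | 8 weeks = 56 days | Appendix H, Budesonide |
| Limit on concomitant or recent dose | 9 mg/day | Protocol Summary; 4.3 no. 8; 8.1 |
| Taper step | 3 mg off the daily dose | 6.7 |

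The last two rows govern use around screening and on study, not past exposure. They are used here only to show the dose scale on which the protocol works.

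**Conversion.** 9 g × 1000 mg/g = 9000 mg.

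**Read as a daily dose.** 9000 mg ÷ 9 mg = 1000. The threshold is 1000 times the largest daily budesonide dose stated elsewhere in the visible protocol.

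**Read as a cumulative dose.**

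- Amount delivered by the minimum course at 9 mg/day: 9 × 56 = 504 mg = 0.504 g.
- Time to reach 9 g at 9 mg/day: 9000 ÷ 9 = 1000 days; 1000 ÷ 7 = 142.9 weeks.
- Ratio to the minimum course: 1000 ÷ 56 = 17.9.
- Daily dose needed to accumulate 9 g in exactly 8 weeks: 9000 ÷ 56 = 160.7 mg/day, again 17.9 times 9 mg/day.

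Eight weeks is a minimum, so the cumulative reading is not impossible: a subject treated for about 1000 days at 9 mg/day would meet it. It is unworkable as a general rule on this dose scale.

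**Does the local-practice clause settle it?** The clause sits under systemic corticosteroids and refers to the definition of failure given there. The budesonide entry points to that section for intolerance only, and criterion 9 lists budesonide separately from systemic corticosteroids. On the wording, the clause does not clearly extend to budesonide failure.

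**Does anything else in the plan move?** The ITT and safety populations (Protocol 9.2; SAP 5.3.1 and 5.3.3) are defined by randomization and at least one dose, not by eligibility route. The Table 5 powers reproduce with a two-proportion calculation at two-sided 0.05:

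- 22% v 36% with 266 v 798 subjects: 99.3% (stated 99%)
- 22% v 36% with 266 per group: 94.7% (stated 95%)
- 10% v 20% with 266 per group: 90.0% (stated 90%)

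None of these uses the Appendix H text.

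**The case against.** The strongest reply is that this is a one-word slip that any gastroenterology site would see through. Both literal readings are so far off the protocol's scale that nobody would apply them, and the documents show no site or monitor doing so. That may well describe practice. But it means departing from the written criterion by an unwritten rule, and it leaves the time basis open.

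Other points deserve weight:

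- The comparison doses are upper limits or taper steps, whereas Appendix H sets a lower bound on past exposure. They are different kinds of rule. This stands, and it is why they are used for scale only. Parts of the protocol are also redacted, so the comparison covers visible doses.
- The missing time basis is not peculiar to budesonide. Appendix H also gives none for azathioprine or 6-mercaptopurine, and the prednisone unit is garbled. This stands too, but only the budesonide entry departs from the protocol's own scale by a factor of 1000.
- The local-practice clause speaks of steroids generally, the protocol elsewhere groups budesonide with oral corticosteroids, and an amendment summary describes the change as concerning steroid failure. Wider intent is possible; the operative text does not state it.
- The study was terminated early (SAP Section 2), so a correction guides no future enrolment. This limits the benefit to reporting but does not remove it, because both SAP tables are still planned.

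**Conclusion.** The point holds. The budesonide-failure threshold is wrong or unusable as written: 1000 times the protocol's daily scale if read as a daily dose, or 1000 days of treatment at 9 mg/day if read as cumulative. The size rests on taking 9 mg/day, the largest daily budesonide dose visible elsewhere, as the reference.

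The reach is narrow. Only subjects whose sole qualifying history is budesonide failure are affected; budesonide intolerance and the corticosteroid, immunosuppressant and biologic routes are not. The documents do not give the number of such subjects, and it could be zero. No analysis population or power figure changes, and no efficacy estimate in the visible plan is altered. Confidence is high on the wording error; its practical consequence cannot be sized from the documents. It should be corrected, but it does not threaten the trial's conclusions.

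**What to change.** Reconcile the unit and time basis in the Appendix H budesonide entry with the Protocol Summary, exclusion criterion 8, Section 6.7 and Section 8.1. Which figure is right is for the sponsor's clinical team to settle. State at the same time whether the local-practice clause under systemic corticosteroids also applies to budesonide failure. The missing time bases for azathioprine and 6-mercaptopurine and the garbled prednisone unit can be checked in the same edit.

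Then classify subjects whose only qualifying history is budesonide failure against the reconciled text, by one documented rule, when the SAP Section 6 and Section 7 tables are produced.

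The cost is a one-line clarification or note to file, plus a record check confined to those subjects. No reanalysis is needed.

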### Systemic corticosteroids

- Failure is defined as having signs and symptoms of active disease despite a history of receiving at least one 4-week course regimen with prednisone  $\geq 0.75$  mg/kg mg daily orally or equivalent, or 1 week of intravenous corticosteroids. Where regional or local practice standards for the use of steroids in CD differ from this definition of failure, the local or regional standard should be used.
- Intolerance includes, but is not limited to Cushing's syndrome, osteopenia/osteoporosis, hyperglycemia, insomnia and infection.

[figure not shown]
### Immunosuppressants

- Failure is defined as signs and symptoms of active CD despite a history of  $\geq 8$  weeks of treatment with azathioprine ( $\geq 1.5$  mg/kg), or 6-mercaptopurine ( $\geq 0.75$  mg/kg), or methotrexate ( $\geq 12.5$  mg/week)
- Intolerance includes, but is not limited to nausea, vomiting, abdominal pain, pancreatitis, liver function test abnormalities, lymphopenia and infection

### Biologics

- Failure is defined by:
  - an inadequate initial response (primary nonresponder) after at least 2 doses of induction therapy to: infliximab (doses of  $\geq 5$  mg/kg); adalimumab (doses of 160 mg followed by 80 mg); certolizumab (doses of 400 mg) or vedolizumab (doses of 300 mg) at least 2 weeks apart, or
  - recurrence of signs and symptoms, such as worsening of diarrhea, abdominal pain, rectal bleeding, or initiation or increased use of antidiarrheals (secondary nonresponders) after at least 2 doses of maintenance therapy to infliximab (doses of  $\geq 5$  mg/kg), adalimumab (doses of 40 mg), certolizumab (doses of 400 mg); or vedolizumab (doses of 300 mg).
- Intolerance to biologics may include fever, chills, rash, flush, itching, hypotension, urticaria, myalgia, arthralgias; which were related to the treatment.

[Redacted text block containing multiple paragraphs of obscured content]

CEL GENE PROPRIETARY INFORMATION

[REDACTED]

[REDACTED]

[REDACTED]

[REDACTED]

[REDACTED]

[REDACTED]

[REDACTED]

[REDACTED]

[REDACTED]

[REDACTED]

[REDACTED]

[REDACTED]

[REDACTED]

[REDACTED]

[REDACTED]

[REDACTED]

[REDACTED]

CELGENE PROPRIETARY INFORMATION

## APPENDIX M. HALF LIVES OF BIOLOGICS

**Table 8: Elimination Half Lives of Biologics**

| Biologic | 1 Elimination Half Life | 5 Elimination HalfLives |
|-----------------|--------------------------------|--------------------------------|
| Infliximab      | 10 days                        | 50 days                        |
| Adalimumab      | 20 days                        | 100 days                       |
| Certolizumab    | 14 days                        | 70 days                        |
| Vedolizumab     | 25 days                        | 125 days                       |

\* Note: The half-life information was obtained from the package insert of each above-mentioned biologics.

CELGENE PROPRIETARY INFORMATION

## **APPENDIX O: CRITERIA FOR TEMPORARY INTERRUPTION OF IP OR STUDY DISCONTINUATION BASED ON LIVER FUNCTION TEST ABNORMALITIES**

Criteria for discontinuing or temporarily interrupting study treatment:

- When the baseline values were  $< 2$  x upper limit of normal (ULN), discontinue if alanine aminotransferase (ALT) or aspartate aminotransferase (AST) increases to  $> 5$  x baseline values.
- When the baseline values were  $\geq 2$  x ULN but  $< 5$  x ULN, discontinue if ALT or AST increases to  $> 3$  x baseline values.
- When ALT or AST increase  $> 2$  x baseline values AND the increase is accompanied by a concomitant total bilirubin (TBL) increase to  $> 2$  x baseline values.
- All patients who develop symptoms consistent with hepatic injury (eg, appearance of fatigue, nausea, vomiting, right upper quadrant pain or tenderness, fever, rash, and/or eosinophilia [ $> 5\%$ ]) in combination with elevations in liver enzymes.

